5.3 Randomization Standard

Subjects who do not meet the eligibility criteria shall not be enrolled in this study with no exceptions. In the event that an ineligible subject is randomized, or the treatment erroneously starts, or an enrolled subject no longer meets the eligibility criteria before starting the study treatment, the sponsor's medical representative and the investigator must jointly discuss whether the subject should continue or withdraw from the study. The sponsor should ensure that appropriate documentation is retained with regards to such decisions.

Subjects who have failed previous screening may be screened again in this study. The informed consent form should be re-signed and a new subject number should be given for re-screening. The treatment will start within 24 hours after randomization.

5.4 Withdrawal from Study or Treatment Discontinuation

5.4.1 Study withdrawal criteria

Reasons for withdrawal may include:

1. The subject withdraws the ICF and refuses further follow-ups
2. Any clinical adverse drug reactions, laboratory abnormalities, or complications that renders the subject not benefiting from further treatment, as determined by the investigator
3. Other reasons investigator deems necessary for withdrawal, such as the inability to provide voluntary consent due to imprisonment or quarantine
4. Lost to follow-up
5. Death
6. Study termination by the sponsor

5.4.2 Criteria for treatment discontinuation

The study treatment must be discontinued when any of the following occurs:

1. Subject requests to discontinue the study treatment
2. Radiographic or clinical evidence of progressive disease, unless the subject meets the criteria for continuing treatment beyond progression (see 6.1.2 of the protocol)
3. Occurrence of pregnancy during the study
4. Any clinical AEs, laboratory abnormalities, or other medical conditions indicating that the subject can no longer benefit from the treatment

5. General deterioration of health status suggesting that the subject cannot continue to involve the study
6. The enrolled subject is found to have important protocol deviations such as ineligibility
7. Lost to follow-up
8. Study termination by the sponsor
9. Death
10. Other reasons as determined by the investigator

5.4.3 Procedures for withdrawal or discontinuation

The end-of-treatment efficacy and safety examinations, safety follow-up, and survival follow-up as specified in the protocol must be completed as much as possible, and the AEs and their outcomes should be fully documented. The investigator can recommend or provide new or alternative treatments to a subject based on the condition of the subject. For subjects who discontinue the treatment for reasons other than radiologically confirmed PD, imaging evaluations shall be performed as much as possible per the scheduled time points until any of the following events occurs: start of new anti-tumor therapy, PD, withdrawal of ICF, or death.

Subject's survival status should still be followed up even when the subject refuses to visit the study center, unless the subject withdraws consent to provide further information or consent to be further contacted. In such case, no study assessment is performed, nor any data are collected. The sponsor can retain and continue to use all data collected prior to withdrawal of ICF, unless the subject requests a retraction of collected data.

5.5 Termination or Suspension of Study

This study can be terminated early or suspended if there are sufficient reasons. This may result from the decision of the regulatory authorities, changes in comments by the Ethics Committee, efficacy or safety issues of the study medications, or the judgment of the sponsor. In addition, Hengrui reserves the right to terminate the research and development of the investigational drug at any time. The party who decides to suspend/terminate the study should notify the investigator, sponsor, and regulatory authorities in writing, documenting the reasons for suspension/termination. The investigator must immediately notify the ethics committee and sponsor, and provide relevant reasons.

The reasons for termination or suspension of the study may include:

1. Confirmed unexpected, major, or unacceptable risk to the subjects
2. Existing efficacy data supporting study termination
3. Poor protocol compliance
4. Incomplete or undetectable data
5. Valueless study results

6 STUDY DRUGS

6.1 Treatment Regimen

6.1.1 Administration regimen

Study drugs refer to SHR-1210 and apatinib, and other drugs during the study are non-study drugs. Refer to [Table 5](#) for the treatment regimen. For the ease of liquid preparation, the protocol allows a deviation of $\pm 5\%$ between the actual dosage and the theoretical dosage each time.

The study drugs will be administered until PD (refer to Section 6.1.2 for continued medication beyond progression), intolerable toxicity, withdrawal of ICF, other reasons that require treatment discontinuation (whichever occurs first)

Table 5. Treatment regimen

Phase	Drug	Dose	Route of Administration	Administration Cycle
II	SHR-1210	200 mg	IV	Q2W
	Apatinib, combined	375 mg	PO	QD
	SHR-1210	200 mg	IV	Q2W
	Apatinib, combined	375 mg	PO	QD (5 days on, 2 days off)
	SHR-1210	200 mg	IV	Q2W
	Apatinib, combined	375 mg	PO	QD (7 days on, 7 days off)

Note:

1. On the day of SHR-1210 infusion, apatinib shall be administered 30 min after the end of SHR-1210 infusion.
2. SHR-1210 is administered through intravenous drip infusion at 200 mg once every 2 weeks with 4 weeks as 1 treatment cycle.
3. Apatinib is administered orally once daily after meal with 4 weeks as 1 treatment cycle. Subjects are randomized into the three groups in a 1:1:1 ratio. Drugs should be administered at a fixed time every day as much as possible.
4. PO: per os; QD: quaque die; IV: intravenous infusion; Q2W: once every 2 weeks; 5 Days on, 2 Days off: administration for 5 days and interrupt for 2 days; 7 Days on, 7 Days off: administration for 7 days and interrupt for 7 days

6.1.2 Continued medication beyond progression

Subjects are allowed to continue the original regimen of study treatment after the initial PD confirmed as per RECIST v1.1, provided that the following conditions are met:

1. Investigator-assessed clinical benefit, and
2. Tolerability in the subject

Investigator-assessed clinical benefit and tolerability in the subject are based on the following considerations:

1. No significant clinical symptoms and changes in laboratory parameters
2. No change (deterioration) in the score of performance status
3. No rapid tumor progression and no tumor progression involving vital organs/sites (such as metastases to central nervous system, respiratory failure due to tumor compression, and spinal cord compression)

For subjects who continue the original regimen of study treatment after progression, the investigator must reassess the benefits and risks of the subject. The ICF must be re-signed. The longest duration of SHR-1210 administration is 2 years.

An additional imaging evaluation must be performed in 4 weeks (+ 7 days) for confirmation after the initial documentation of imaging PD. If PD is not radiographically confirmed, the original study medication and imaging evaluation can be continued until relapse of PD (refer to Section 8.1.2 of the protocol). Subjects with relapse of PD must discontinue treatment.

6.1.3 Continued treatment after study completion

Study completion is defined as 180 days after the first dose of the last subject.

Upon completion of the study, subjects who still benefit clinically may continue the study treatment provided by Hengrui until the criteria for discontinuation are met, and will be continuously followed for OS events. The study drug is provided through extension studies, rollover studies approved by the health regulatory authorities and ethics committee, or other ways determined by Hengrui.

Hengrui reserves the right to stop providing the study drugs in any of the following cases: a) rejection of marketing application by health regulatory authorities; b) termination of the study due to safety issues; c) subjects able to obtain the study drugs from a public or privately-sponsored medical plan; or d) available replacement therapies in the local market.

6.2 Study Drugs

6.2.1 Description

The following study drugs will be supplied by the sponsor in a centralized manner. Refer to [Table 6](#) for the description of study drugs.

Table 6. Description of study drugs

Name	SHR-1210 for injection	Apatinib mesylate tablets
Manufacturer	Suzhou Suncadia Biopharmaceuticals Co., Ltd.	Jiangsu Hengrui Pharmaceuticals Co., Ltd.
Appearance	White or off-white lyophilized powder	Film-coated tablet, white or off-white after peeling off coating
Route of Administration	Intravenous injection	Oral
Strength	200 mg/20 mL vial	250 mg/tablet; 375 mg/tablet
Storage and Stability	Placed in a 2-8 °C medical refrigerator during storage and the shelf life is tentatively set to 2 years. Do not freeze	Sealed and stored below 25 °C and kept away from light. Valid for 2 years

6.2.2 Packaging and labeling of study drugs

The sponsor will package and label the study drug in accordance with local regulatory requirements.

6.3 Study Drug Preparation

The study drugs should be prepared by qualified or experienced study staff (such as physicians, pharmacists, or medical assistants) according to the drug brochures or package inserts (approved by national authorities or study center operating guidelines).

6.3.1 SHR-1210

SHR-1210 is a lyophilized powder for injection that needs to be prepared before its administration via intravenous drip infusion. Refer to Drug Manual for the preparation of SHR-1210.

6.4 Dose Modifications and Delay

6.4.1 General rules for dose modification

- Reasons for dose modification or dose delay, actions taken, and results should be recorded in the medical record and eCRF of the subject.
- For the accompanying symptoms that existed at baseline, the investigator shall determine whether to adjust the dose according to the grade of adverse drug reactions. For example, at baseline, a subject's Grade 1 "asthenia" at baseline that becomes Grade 2 "asthenia" during the study treatment period is one level increase of "asthenia". The dose should be adjusted as a Grade 1 toxicity

- If several adverse drug reactions of different grades or severity occur at the same time, the dose will be adjusted based on the highest level observed.
- If the dose is adjusted only due to abnormal hematological values, the dose will be adjusted based on the hematological values before the start of the treatment cycle.
- When the investigator judges that the adverse drug reaction is unlikely to further develop into a serious or life-threatening event, the current dose will be continued without dose modification or treatment interruption. In addition, no dose modification or treatment interruption is administered for anemia (non-hemolytic) because its symptoms can be relieved through blood transfusion.
- If, per the investigator's judgment, the toxic reaction is caused by a therapeutic drug, there is no need to adjust the dose of other drugs.
- Before PD, permanent discontinuation of a medication will not affect the continued administration of other treatments.
- If any treatment but not all drugs is interrupted due to adverse drug reactions of a drug, the treatment is still counted as a treatment cycle.

6.4.2 Apatinib

Dose interruption of apatinib is allowed for up to 4 weeks (from the actual time of last dose); otherwise the treatment of apatinib shall be discontinued. A maximum of one dose modification is allowed; otherwise the subject will be considered intolerable and the treatment of apatinib shall be discontinued. Refer to [Table 7](#) for the requirements of dose modification of apatinib.

Table 7. Requirements of dose modification of apatinib

Adverse Drug Reaction	Grade	Whether to Interrupt Treatment	Rules for Dose Modification
Hematologic	Grade 1-2	No	—
	Grade 3	Yes	
• For the first occurrence, interrupt the treatment until the adverse drug reactions recover to Grade ≤ 2, and resume the treatment at the original dose• For the second occurrence, interrupt the treatment until the adverse drug reactions recover to Grade ≤ 2, and resume the treatment at a reduced dose of 250 mg/d• For recurrence after dose reduction, the investigator should evaluate the risks/benefits of the continued apatinib treatment and determine whether the drug should be permanently discontinued

Adverse Drug Reaction	Grade	Whether to Interrupt Treatment	Rules for Dose Modification
	Grade 4	Yes	
Resume the treatment at a reduced dose of 250 mg/d after the adverse drug reactions recover to Grade ≤ 2For the recurrence of Grade 4 toxicity after dose reduction, the treatment shall be permanently discontinued
Non-Hematological	Grade 1	No	—
	Grade 2 (lasting for ≥ 7 d)	Yes	
Resume the treatment at the original dose after the adverse drug reactions recover to Grade ≤ 1
	Grade 3	Yes	
For the first occurrence, interrupt the treatment until the adverse drug reactions recover to Grade ≤ 1, and resume the treatment at the original doseFor the second occurrence, interrupt the treatment until the adverse drug reactions recover to Grade ≤ 1, and resume the treatment at a reduced dose of 250 mg/dFor recurrence after dose reduction, the investigator should evaluate the risks/benefits of the continued apatinib treatment and determine whether the drug should be permanently discontinued
	Grade 4	Yes	
Resume the treatment at a reduced dose of 250 mg/d after the adverse drug reactions recover to Grade ≤ 1For the recurrence of Grade 4 toxicity after dose reduction, the treatment shall be permanently discontinued

In the case of the following circumstances, the measures to be taken for apatinib (the following grades are per CTCAE v4.03) are described as follows; if necessary, relevant departments should be consulted:

Hemorrhage

- Grade 3 or 4 bleeding should be treated accordingly and apatinib treatment should be permanently discontinued

Thrombosis/embolism

- For arterial thrombosis of any grade, apatinib treatment should be permanently discontinued
- For Grade 4 venous thrombosis, apatinib treatment should be permanently discontinued
- For Grade 3 venous thrombosis, apatinib treatment should be interrupted. For anticoagulant therapy at the planned therapeutic dose for ≤ 2 weeks, apatinib treatment should be interrupted until the end of anticoagulant therapy. For anticoagulant therapy at

the planned therapeutic dose for > 2 weeks, apatinib treatment should be interrupted for 2 weeks until the following criteria are met, and the study treatment may be resumed during the anticoagulant treatment:

- Before the resumption of study medication, the INR should be within the target range (usually 2-3)
- Subjects should not have Grade 3 or 4 bleeding events since study enrollment
- No finding of tumor invasion or adjacency to large blood vessels in previous tumor evaluations

Note: Therapeutic dose of anticoagulant therapy is defined as the gradual escalation of the dose of warfarin or other anticoagulants to a dose level that maintains an INR not less than 1.5 (usually 2-3). The dose of warfarin should be recorded in the eCRF, and the INR should be monitored throughout the treatment period for subjects receiving anticoagulant therapy.

Hypertension

The blood pressure should be regularly measured in order to monitor the occurrence and deterioration of the subject's hypertension.

- Grade 1: Prehypertension (systolic blood pressure of 120-139 mmHg, diastolic blood pressure of 80-89 mmHg), no intervention is needed.
- Grade 2: First-stage hypertension (systolic blood pressure of 140-159 mmHg, diastolic blood pressure of 90-99 mmHg), medical intervention is required; repeated or persistent (≥ 24 h), an increase in symptomatic systolic blood pressure by > 20 mmHg, or an increase in blood pressure within the normal range to $> 140/90$ mmHg. Apatinib treatment should be interrupted. An antihypertensive drug may be used for treatment. Once the blood pressure is controlled to $< 140/90$ mmHg, the subject may continue the apatinib treatment.
- Grade 3: Second-stage hypertension (systolic blood pressure of ≥ 160 mmHg, diastolic blood pressure of ≥ 100 mmHg), more than one antihypertensive drug or a higher intensity treatment are required. For persistent or symptomatic hypertension, apatinib treatment should be interrupted; if hypertension is still uncontrollable after 4 weeks of treatment, apatinib treatment should be permanently discontinued.
- Grade 4: Life-threatening (malignant hypertension or persistent nerve damage, hypertensive crisis) emergency intervention, life-threatening (such as hypertensive crisis). For Grade 4 hypertension, apatinib treatment should be permanently discontinued. The dose of antihypertensive drugs used should be recorded at each visit.

The dose of antihypertensive drugs used should be recorded at each subject visit of the subjects. If hypertension still persists when the treatment is discontinued, blood pressure and the use of antihypertensive drugs should be monitored every 3 months until the blood pressure returns to normal or the study completion.

Reversible posterior leukoencephalopathy syndrome (RPLS)

Symptoms and signs consistent with RPLS are rarely reported in subjects receiving the drug treatment. This is a rare neurological disease. The symptoms and signs are: epilepsy, headache, mental status changes, visual disturbance, or cortical blindness, with or without hypertension. Once a subject develops RPLS, apatinib treatment should be permanently discontinued.

Proteinuria

Follow the schedule of study procedures for urinalysis, if:

- < 2+, continue the administration of apatinib as planned, no additional tests are required
- $\geq 2+$, immediately monitor the 24-hour urine protein. 24-hour urine protein:
 - < 1 g, continue apatinib treatment as planned
 - 1-3.4 g, interrupt the apatinib medication until the 24-hour urine protein is < 1 g, and then resume the apatinib treatment. For the second occurrence, interrupt apatinib treatment until the 24-hour urine protein is < 1 g, and reduce the dose to 250 mg/d. For recurrence after dose reduction, the investigator should evaluate the risks/benefits of the continued apatinib treatment and determine whether the drug should be permanently discontinued
 - ≥ 3.5 g or occurrence of nephrotic syndrome, apatinib treatment is permanently discontinued

6.4.3 SHR-1210

Dose increase or reduction for SHR-1210 is prohibited. Only interruption or permanent discontinuation is allowed. Dose interruption of SHR-1210 is allowed for up to 8 weeks (from the actual time of last dose); otherwise the treatment of SHR-1210 shall be discontinued. For SHR-1210 interruption that exceeds 8 weeks, the investigator should discuss with the sponsor's medical department if he/she judges that the subjects can benefit from continued treatment.

Refer to [Table 8](#) for the requirements on dose modification of SHR-1210. Refer to Appendix 6 for the guidelines on dose modifications and handling of toxicities of SHR-1210. Refer to [Table 9](#) for the treatment of SHR-1210 related infusion reactions.

In addition, treatment should be discontinued permanently if PD is determined by the investigator as per the RECIST v1.1 criteria (unless subjects meet the criteria for continued treatment after PD as described in Section 6.1.2 of the protocol). For treatment interruption due to medical events, surgeries, or unexpected (holidays) events unrelated to the study treatment, the subject should resume study treatment within 2 weeks after interruption (i.e., originally scheduled administration time), unless otherwise jointly determined by the investigator and the sponsor. The reasons for treatment interruption should be documented in the eCRF.

Table 8. Principles for SHR-1210 dose modification

Adverse Drug Reaction	Severity	Dose Modification
Pneumonia	Grade 2 pneumonia	Treatment interruption ^a
	Grade 3 or 4 pneumonia	Permanent discontinuation
Diarrhea/Enterocolitis	Grade 2 or 3 diarrhea or enterocolitis	Treatment interruption ^a
	Grade 4 diarrhea or enterocolitis	Permanent discontinuation
Dermatitis	Grade 3 dermatitis	Treatment interruption ^a
	Grade 4 dermatitis	Permanent discontinuation
Hepatitis	For subjects with normal baseline ALT, AST, or TBIL, Grade 2 AST, ALT, or TBIL increased, or For subjects with baseline AST, ALT, or TBIL > ULN, AST, ALT, or TBIL increased by ≥ 50% persisting for < 7 days	Treatment interruption ^a
	For subjects with normal baseline ALT, AST, or TBIL, Grade 3 or 4 AST, ALT, or TBIL increased, or For subjects with baseline AST, ALT, or TBIL > ULN, AST, ALT, or TBIL increased by ≥ 50% persisting for ≥ 7 days	Permanent discontinuation
	Grade 2 hypophysitis	Treatment interruption ^b
	Grade 3 or 4 hypophysitis	Permanent discontinuation
Adrenal cortical insufficiency	Grade 2 adrenal cortical insufficiency	Treatment interruption ^b
	Grade 3 or 4 adrenal cortical insufficiency	Permanent discontinuation
Hyperthyroidism	Grade 3 or 4 hyperthyroidism	Permanent discontinuation

Adverse Drug Reaction	Severity	Dose Modification
Type 1 diabetes	Grade 3 hyperglycemia	Treatment interruption ^b
	Grade 4 hyperglycemia	Permanent discontinuation
Kidney dysfunction	Grade 2 or 3 creatinine increased	Treatment interruption ^a
	Grade 4 creatinine increased	Permanent discontinuation
Neurotoxicity	Grade 2 neurotoxicity	Treatment interruption ^a
	Grade 3 or 4 neurotoxicity	Permanent discontinuation
Infusion reactions	Grade 3 or 4 infusion reaction	Permanent discontinuation
Other AEs	First occurrence of other Grade 3 AE	Treatment interruption ^a
	Second occurrence of the same Grade 3 AE	Permanent discontinuation
	Grade 3 AEs that cannot recover to Grade 0-2/baseline level within 7 days or recover to Grade 0-1/baseline level within 14 days	Permanent discontinuation
	Grade 4 AE	Permanent discontinuation ^c

Note:

- a: Resume the medication after the symptoms improve to Grade 0-1 or the baseline level.
- b: For hypophysitis, adrenal insufficiency, and type 1 diabetes, medication may be resumed if the AEs are fully controlled and only require physiological hormone replacement therapy.
- c: For Grade 4 abnormal laboratory findings, the decision of treatment discontinuation should be based on the accompanying clinical symptoms/signs and the clinical judgment of the investigator.

Table 9. Treatment recommendations for infusion reactions of SHR-1210

CTCAE Grade	Dose Modification	Treatment of Toxicity
Any Grade		
 - Treat according to local clinical practice - Monitor the subject's infusion-related reactions (e.g., pyrexia or shivers, flushing and/or pruritus, changes in heart rate and blood pressure, dyspnea, chest discomfort, and rash) and allergic reactions (e.g., generalized urticaria, angioedema, asthma, hypotension, and tachycardia)

CTCAE Grade	Dose Modification	Treatment of Toxicity
Grade 1	The infusion rate may be reduced by 50% or the infusion can be temporarily interrupted until the infusion reaction is relieved	For Grade 1 or 2: 
- Give acetaminophen and/or antihistamines at the discretion of the investigator based on local clinical practice- Consider prophylactic medication before subsequent courses of treatment according to local clinical practice
Grade 2	The infusion rate may be reduced by 50% or the infusion can be temporarily interrupted until the infusion reaction is relieved. The subsequent infusion rate can be adjusted to 50% of the initial rate	
Grade 3/4	Permanent discontinuation	For Grade 3 or 4: 
- Deal with severe infusion-related reactions according to local clinical practice (e.g., administration of epinephrine, diphenhydramine, ranitidine, and glucocorticoids)

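### For immune-related events, Table 8 and Appendix 6 give different SHR-1210 restart rules in at least two rows (creatinine and Grade 3 dermatitis), and Section 6.4.3 does not say which applies

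*Protocol*

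**What the plan says.** Section 6.4.3 cites Table 8 "for the requirements on dose modification of SHR-1210" and then says "Refer to Appendix 6 for the guidelines on dose modifications and handling of toxicities of SHR-1210". It gives no order of precedence. It limits any SHR-1210 interruption to 8 weeks from the last dose, with one opening: "For SHR-1210 interruption that exceeds 8 weeks, the investigator should discuss with the sponsor's medical department" if continued benefit is expected.

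**Table 8.** The kidney row interrupts SHR-1210 for "Grade 2 or 3 creatinine increased" under note a and stops it permanently for "Grade 4 creatinine increased". The Grade 3 dermatitis row also interrupts under note a. Note a reads: "Resume the medication after the symptoms improve to Grade 0-1 or the baseline level". Neither row states a time limit. The Other AEs rows carry a separate Grade 3 limit: permanent discontinuation unless the event is down to Grade 0-2 within 7 days and Grade 0-1 within 14 days (or baseline in either case).

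**Appendix 6.** Its General Rules direct the reader there once an event is judged immune-related, but describe the content as recommended. A Grade 2-3 creatinine event that lasts more than 7 days or worsens is handled as Grade 4. A Grade 3 rash that has not returned to Grade 0-1 or baseline within 30 days ends SHR-1210 permanently.

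**The concern.** Both sources cover the same toxicities, and Table 8 does not exclude immune-related events. An investigator whose patient has recovered late from a renal or skin reaction can therefore find one page that restarts SHR-1210 and another that forbids it. The cues on precedence pull in opposite directions: Section 6.4.3 calls Table 8 the requirements, while Appendix 6 claims immune-related events for itself.

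At stake is re-exposure after a renal or skin immune reaction or, in the other direction, withdrawal of a drug that the other page would still allow. With about 20 centres, practice could differ between sites. SAP Section 5.3.1 summarises SHR-1210 interruptions and permanent discontinuations with their reasons, so inconsistent handling would also reach those descriptive tables.

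**Working it through.** The plan states no figure here to reproduce. The check is a comparison of the two texts, followed by simple day counts.

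**Step 1: what Grade 4 handling means for creatinine.** The renal rows of Appendix 6 are misaligned in the available text, and the Grade 4 dosing cell cannot be read. The step does not need that cell. Grade 4 creatinine is permanent discontinuation in Table 8, and that row does not carry note c (clinical judgement for Grade 4 laboratory findings). Grade 4 is also permanent discontinuation in the Appendix 6 General Rules. The 7-day bullet can be placed despite the misalignment: it is labelled for Grade 2-3 and paired with a bullet on restarting after improvement to Grade 0-1, so it concerns dosing at those grades.

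**Step 2: inputs for the day counts.**
- Cap on interruption: 8 weeks = 56 days from last dose (Section 6.4.3), taken as firm.
- Days from last dose to onset: t = 0 to 14. This is an assumption based on Q2W dosing.
- Appendix 6 limits: 7 days (creatinine) and 30 days (Grade 3 rash), assumed to run from onset.
- Latest recovery that Table 8 accepts, counted from onset: 56 − t = 42 to 56 days.

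**Step 3: windows with opposite answers.** In the first reading, the 7/14-day limit belongs to the Other AEs rows only. In the second, it covers every Grade 3 event.

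| Event | First reading | Second reading |
|---|---|---|
| Grade 2 creatinine | 42 − 7 = 35 to 56 − 7 = 49 days, Table 8 looser | unchanged, because the limit concerns Grade 3 |
| Grade 3 creatinine | 35 to 49 days, Table 8 looser | 14 − 7 = up to 7 days, Table 8 looser |
| Grade 3 dermatitis | 42 − 30 = 12 to 56 − 30 = 26 days, Table 8 looser | 30 − 14 = 16 to 30 − 7 = 23 days, Table 8 stricter |

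The 23 days apply to a rash still at Grade 3 after day 7, which fails the first branch of the limit. The 16 days apply to one that passes day 7 but not day 14.

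**Step 4: examples.** An immune-related Grade 2 creatinine rise returns to Grade 1 on day 10: Table 8 restarts and Appendix 6 stops for good. A Grade 3 rash recovers on day 35, which is 35 to 49 days after the last dose and so inside the cap: on the first reading Table 8 restarts and Appendix 6 stops. A Grade 3 rash recovers on day 20: on the second reading Table 8 stops and Appendix 6 restarts.

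**Step 5: other rows.** For Grade 2 hypophysitis and adrenal insufficiency, Table 8 note b permits restart once the event is controlled on physiological hormone replacement. Appendix 6 asks for Grade 0-1 or baseline. The wording differs, so the count above is at least two rows. By contrast, the hepatitis limit for abnormal baseline values ("TBIL increased by ≥ 50% persisting for ≥ 7 days") appears in both sources, so Table 8 can carry such a limit.

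**The case against.** The best answer is that silence is not contradiction. Note a gives a recovery condition and need not be the whole restart rule; the 8-week cap is already read into it from the text outside the table. Appendix 6 limits can be added in the same way, and its scope line invites that for immune-related events. A site that applied both sources together would have a workable rule.

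That reading is reasonable, but the protocol does not state it. Note a is worded as an instruction to resume, Table 8 is called the requirements, and Appendix 6 calls itself recommended. If the 7/14-day limit covers dermatitis, applying both sources would also leave the 30-day rule with nothing to do. The hepatitis row does not settle intent either; it concerns only patients with abnormal baseline values.

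Two further parts of the objection stand. First, a reader might infer from the printed order that sponsor discussion of creatinine is asked for only at Grade 4. The misaligned renal rows do not support that: two similar lists of steps run together there, and the first may belong to Grade 2-3. Second, a reader might infer that the remedy is to let Appendix 6 prevail for all immune-related events. That would displace the Other AEs stopping rules in Table 8 (second occurrence of the same Grade 3 event, and the 7/14-day limit) for immune-related events with no row of their own in Appendix 6. There, the General Rules leave Grade 3 as either interruption or permanent discontinuation.

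**Conclusion.** The point holds: two stated rules give different restart decisions for the same immune-related event, and Section 6.4.3 does not choose between them. It is clearest for Grade 2 creatinine, where no reading of the Other AEs limit removes the conflict. For Grade 3 dermatitis the pages disagree on either reading, but the direction reverses, so Table 8 cannot be called the looser source throughout.

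The windows are 35 to 49 days (creatinine) and 12 to 26 days (dermatitis), or 16 to 23 days the other way for dermatitis. They rest on onset 0 to 14 days after a dose, clocks running from onset, and a firm 8-week cap. Sponsor-agreed extension beyond the cap would widen the windows in which Table 8 is the looser source and the cap sets the upper end. The documents give no event rates, so the number of patients affected cannot be estimated.

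A reader might infer that the plan allows dosing through active toxicity. It does not: both sources interrupt SHR-1210 and require recovery first, so the dispute is about late restart. Nor does it reach sample size or the ORR rule; beyond safety handling, only descriptive exposure counts are touched. This is wrong as written, on a minor patient-safety point.

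**What to change.** First, have the sponsor confirm whether the 7/14-day limit is confined to the Other AEs rows, and say so in Table 8. If it was meant to cover dermatitis, the 30-day footnote below would loosen it. Then:

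- Footnote the Table 8 Grade 2-3 creatinine row: if immune-related and lasting more than 7 days, treat as Grade 4, i.e. permanent discontinuation.
- Footnote the Table 8 Grade 3 dermatitis row: if immune-related and not back to Grade 0-1 or baseline within 30 days, permanent discontinuation.
- Copy note b into the Appendix 6 Grade 2 hypophysitis and adrenal rows.
- State that the Other AEs stopping rules in Table 8 stay in force for immune-related events without an Appendix 6 row.
- Do not add a blanket precedence sentence.

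The cost is a handful of table edits and a memo to sites. No extra patients or procedures are needed.
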